#### **Description of Study Intervention**

#### **Research Design and Methods:**

#### Research Subjects & Recruitment (Aims 1, 2, and 3)

Subjects: A total of 60 subjects will be recruited: 30 with cannabis use disorder (CUD) and 30 healthy controls (HC) who do not use cannabis. Each HC will be carefully matched to each CUD subject by age, sex, socioeconomic status, education, nicotine use, and other relevant variables. CUD subjects will undergo PET, an optional EEG, and cognitive testing at Day 0 and Day 28. HC will undergo these same measurements at Day 0 only. Some study participants will be also enrolled in HIC # 2000032181 ("SV2A Density Cannabis Use Disorder"), since that study has shared goals and study personnel with our study. We have staff that are common to both studies. If a subject is also enrolled in HIC# 2000032181, common procedures except for PET scanning will be performed once between the two studies (i.e., MRI and cannabis abstinence procedures will not be duplicated). Whichever study the subject first signs up for will be where the abstinence data will be tracked. The subject would sign a release of information to share the information with the other study.

Recruitment and Screening: Subjects will be recruited with clinicians at Yale and in the greater Connecticut community with whom we have a long history of successful collaboration, including long-standing relations with the Yale Psychiatric Hospital inpatient and outpatient services and mental health clinics in the Greater New Haven area, as well as through flyers, public advertisement (newspaper, radio, internet postings), social media, and word of mouth. Subjects will be appropriately compensated for their participation in the study and retained during the cannabis abstinence period using our validated contingency management paradigm.

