# 5 - Study Population

#### 5.1 Inclusion Criteria

A total of 60 subjects will be recruited: 30 with cannabis use disorder (CUD) and 30 healthy controls (HC). Inclusion criteria for all subjects: 1) Age 18-55 years; 2) Voluntary, written, informed consent; 3) Physically healthy by medical history, physical, neurological, ECG and laboratory exams; 5) No personal or first-degree relative history of psychiatric disorders (outside of cannabis use for CUD group); 6) Full scale and verbal IQs > 80 (Wechsler Adult Intelligence Scale, Fourth Edition; WAIS-IV). CUD group: 1) Cannabis use disorder as determined by DSM-5 structured interviews; 2) Urine toxicology evidence of cannabinoid use. Healthy control group: 1) lifetime cannabis exposure less than 20 times, 2) no cannabis use in the past 2 years by self-report, 3) a negative urine drug screen. Controls will be matched to the CUD group by age, sex, socioeconomic status, education, nicotine use, and other relevant variables.

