information provided in each manuscript, we calculated effect sizes for group differences. Observed effect sizes for group comparisons of cannabis users vs. non-users ranged from d= -0.68 to -1.77, with a median of d=-1.11. These effect sizes are consistent with those observed in our preliminary data, which showed a large effect size associated with differences in mGluR5 availability in CB relative to healthy control individuals in the fronto-limbic circuit (d= 1.72). We will evaluate hypothesis 1 (higher mGluR5 availability in cannabis users) using univariate analysis of variance (ANOVA). Assuming  $\alpha$ =0.05 (two-tailed test) and two groups (cannabis vs. control), our proposed sample size of 60 (30 per group) will provide 81.07% statistical power to detect group differences as small as d= 0.82, which is smaller than the median effect size observed in previous literature and that observed in our preliminary data. Data Analysis for Hypothesis 1: As stated, we will conduct a univariate ANOVA to compare mean fronto-limbic [18F]FPEB  $V_T$  between the HC and cannabis groups. Groups will be carefully matched on demographic variables. However, any demographic variables that differ significantly between groups, including notably age and sex, will be considered for entry as additional fixed factors (categorical variables) or covariates (continuous variables). A significant group difference suggestive of higher mGluR5 availability in CUD subjects will be considered supportive of Hypothesis 1. We will also conduct exploratory analyses to examine betweengroup differences in mGluR5 in other regions, including those involved in affective and cognitive dysregulation (e.g., thalamus, striatum, insula), at the same significance level.

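### The plan describes matching of controls in two different ways, and the Aim 1 ANOVA uses neither the pairs nor, normally, the matching variables; the likely cost is a conservative test with some precision uncredited

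*Combined protocol and SAP*

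**What the plan says.** The three descriptions of matching do not agree.

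- Synopsis, Research Subjects & Recruitment: "Each HC will be carefully matched to each CUD subject by age, sex, socioeconomic status, education, nicotine use, and other relevant variables". With 30 subjects in each group, this reads as individual 1:1 matching.
- Section 5.1, Inclusion Criteria: "Controls will be matched to the CUD group by age, sex, socioeconomic status, education, nicotine use, and other relevant variables". The variable list is the same, but the target is the group.
- Section 9.2, data analysis for Hypothesis 1: "Groups will be carefully matched on demographic variables". This is also group wording, and it mentions demographics only.

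The Aim 1 outcome is V_T averaged over the six fronto-limbic regions. The test is stated as "we will conduct a univariate ANOVA to compare mean fronto-limbic [18F]FPEB" V_T between the HC and cannabis groups. On covariates, section 9.2 says "any demographic variables that differ significantly between groups, including notably age and sex, will be considered for entry as additional fixed factors" or, if continuous, as covariates. The power statement treats the groups as independent: "our proposed sample size of 60 (30 per group) will provide 81.07% statistical power" at d = 0.82, two-sided alpha 0.05.

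No section gives a pair identifier, a matching tolerance, a paired test or a mixed model. Section 9.3 is marked not applicable, and sections 9.4.1 to 9.4.3 refer back to 9.2. CUD subjects who relapse (expected 10%) are replaced, with no rule for the control matched to a replaced subject.

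**The concern.** If controls are matched individually on variables related to V_T, the two members of a pair resemble each other and their V_T values are positively correlated. The independent-groups ANOVA assumes that correlation is zero, so it overstates the variance of the CUD minus HC difference.

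The covariate rule does not make up for this. It admits a matching variable only when the groups differ significantly on it, and successful matching is meant to prevent that. Nicotine use, a named matching variable, may not count as demographic at all. In the expected case, the analysis therefore uses neither the pairs nor the variables on which they were formed.

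Aim 1 is the between-group test of the primary endpoint. What is at stake is its efficiency: a confidence interval wider than the design warrants, and a higher chance of missing a difference at the low end of the effect range the plan cites.

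**Working it through.** **Inputs from section 9.2.** n = 30 per group; two-sided alpha 0.05; d = 0.82 for sizing; smallest absolute effect in the plan's literature range, d = 0.68. **Assumption.** The documents give no within-pair correlation, so rho is taken from 0 to 0.5. The upper end is generous: if only the matching variables induce the correlation, rho = 0.5 needs near-exact matching on variables that explain half the variance of V_T.

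**1. The plan's own figure.** A two-group ANOVA is the two-sample t-test with 58 df and noncentrality d × sqrt(n/2) = 0.82 × sqrt(15) = 3.18. Power is 87.8%, not the stated 81.07%; 25 per group gives 81.08%. This is a separate correction. The printed figure understates power, so it does not put the sample size in doubt.

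**2. Standard error under matching.** With common SD σ:

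- variance of the mean difference: 2σ²(1 − rho)/30
- variance the ANOVA uses: about 2σ²/30
- ratio of true to ANOVA standard error: sqrt(1 − rho) = 0.95, 0.89, 0.84 and 0.71 at rho = 0.1, 0.2, 0.3 and 0.5

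**3. Confidence interval.** The ANOVA interval relative to the paired interval is t(58)/[t(29) × sqrt(1 − rho)], with t(58) = 2.002 and t(29) = 2.045:

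- rho 0.2: 2.002/(2.045 × 0.894) = 1.09
- rho 0.3: 2.002/(2.045 × 0.837) = 1.17

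**4. Type I error and power.** Paired power comes from the noncentral t with 29 df and noncentrality sqrt(30) × d/sqrt(2(1 − rho)). ANOVA results for rho above 0 are simulated on bivariate normal pairs and are good to a few tenths of a point.

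| rho | Real type I error of ANOVA | d = 0.68: ANOVA / paired | d = 0.82: ANOVA / paired |
|---|---|---|---|
| 0 | 5.0% | 73.6 / 72.1% | 87.8 / 86.6% |
| 0.1 | 3.9% | 74.6 / 76.5% | 88.9 / 89.9% |
| 0.2 | 2.9% | 75.8 / 81.2% | 90.2 / 92.9% |
| 0.3 | 2.0% | 77.2 / 86.0% | 91.6 / 95.6% |
| 0.5 | 0.7% | 80.9 / 94.9% | 94.6 / 99.1% |

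ANOVA power also rises with rho, because matching shrinks the true variance whether or not the model knows it. The loss is the gap within each cell: about 1 to 5 points at d = 0.82 for rho 0.1 to 0.5, and about 5 and 9 points at d = 0.68 for rho 0.2 and 0.3. At rho = 0 the sign reverses, and a strict paired test costs 1.2 points at d = 0.82 and 1.5 at d = 0.68.

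**5. Broken pairs.** If 10% of pairs (3 of 30) lose a partner and a strict paired test keeps only 27, power at d = 0.82 and rho = 0.2 is 90.0%. That is no better than the ANOVA on all 60 (90.2%), which is why a model that keeps unpartnered subjects is preferable to a paired t-test.

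**The case against.** The strongest reply is that pairing is not established. Only the synopsis describes it; section 5.1 and the analysis text speak of groups, and nothing operational (pair ID, tolerance, replacement rule) exists. Under group matching there are no pairs to model. This stands, and it is why the inconsistency is the first thing to settle. It does not clear the analysis, because under group matching the ANOVA still normally omits the matching variables.

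Second, a reader might infer that the Aim 1 standard error is simply wrong, that the test produces false positives, or that the benefit of matching is thrown away. The documents support none of these. No rho is given, and at rho = 0 the standard error is correct. For rho above 0 the test is conservative, so a significant result remains valid. The precision is only partly lost, as the rising ANOVA power in the table shows.

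Third, the size depends on assumptions. The larger gaps need rho of 0.2 or more together with d = 0.68, and the comparison studies that section 9.2 describes measured CB1, not mGluR5. At the plan's median absolute effect of 1.11, power is 98.8% unpaired and 99.6% paired at rho 0.2. This also stands.

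Fourth, a pair term is not the only remedy. Correlation induced by measured matching variables is removed by adjusting for them, and that works under either kind of matching without a pair ID. This is correct: with individual matching it is an equally sound alternative, provided the adjustment is prespecified and not conditional on a significance test.

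**Conclusion.** The point holds as an inconsistency with a modest, conservative efficiency cost. The synopsis describes a 1:1 matched design, sections 5.1 and 9.2 a group-matched one, and the Aim 1 analysis accounts for neither.

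At an assumed rho of 0.2 to 0.3, the nominal 5% test runs at about 2 to 3% and its interval is 9 to 17% too wide. It gives up about 3 to 4 points of power at d = 0.82. At rho of 0.1 or below, little is lost. These figures rest on the assumed rho, equal variances, normality and 30 complete pairs. The validity of a positive Aim 1 finding is not in question, and the ANOVA does not fall short of the power the plan states. The change is worth making because it is cheap and is best fixed before data are seen.

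**What to change.** State one kind of matching and make the synopsis (Research Subjects & Recruitment), section 5.1 and section 9.2 agree.

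- **If matching is individual:** record a pair ID when each control is matched, and say what happens to a control whose CUD partner is replaced. For Hypothesis 1, replace the univariate ANOVA with a linear mixed model for composite V_T, with group as fixed effect and a random intercept for pair, two-sided 0.05. This keeps subjects without a partner. Unconditional adjustment for all the matching variables is an acceptable alternative.
- **If matching is by group:** correct the one-to-one wording in the synopsis. Always adjust the Hypothesis 1 model for the matching variables, at least age, sex and nicotine use, and drop the rule that admits covariates only on a significant group difference.

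In either case, keep the independent-groups power (rho = 0) as the conservative bound. If a figure that credits the matching is quoted, state its assumed correlation.

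The cost is wording in three places and, for individual matching, one data field; no extra subjects or scans are needed. The downside is about 1 to 1.5 points of power with a strict paired test if matching induces no correlation.

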#### 5.2 Exclusion Criteria

Subjects will be excluded for the following reasons: 1) Other substance use disorder within 1 year, except for nicotine; 2) Another primary DSM-5 Axis I major psychiatric disorder (e.g., schizophrenia, bipolar disorder, major depression, etc.) per SCID-5; 3) Urine toxicology results positive for other drugs such as opiates / opiate metabolites (e.g., methadone, buprenorphine, etc.); 4) A history of significant medical (cardiac, infectious, metabolic) or neurological illness (e.g., cerebrovascular disease, traumatic brain injury); 5) A history of seizures/epilepsy; 6) Medical contraindications to MRI imaging (e.g., ferromagnetic implants/foreign bodies, claustrophobia, etc.); 7) Pregnancy or breastfeeding (women). After completing the informed consent process, subjects will have physical and neurological examinations and an electrocardiogram (ECG). Laboratory tests to be performed at screening to exclude medical illnesses include complete blood count (CBC) and differential, chemistries, kidney function tests [creatinine, blood urea nitrogen (BUN), urinalysis], liver function tests, sex hormones and thyroid stimulating hormone (TSH). Subjects will be excluded for major medical or neurological illness or laboratories consistent with these illnesses or suggesting contraindication to PET or MR imaging. A urine drug screen and a pregnancy test (for women) will be performed before both PET and MRI scans, and subjects excluded for positive screens. Exclusion is subject to PI discretion.

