Aim 2: Within CUD subjects, to examine the associations between mGluR5 availability and: (a) CUD severity; (b) impulsivity; (c) EEG; and (d) neurocognition. Hypothesis 2: Higher mGluR5 availability will be associated with: (a) greater CUD severity (by DSM-5); (b) higher impulsivity; (c) lower theta-band power and LTP, and (d) worse performance on verbal memory. Power Calculations for Hypothesis 2: Using the same standards applied for hypothesis 1, we considered our preliminary data and conducted a literature review to determine what magnitude of correlation we could reasonably expect to see in this study between relevant variables of interest. We included studies with similar methodologies, which reported correlations between similar variables (i.e. similar EEG measures and cognitive/behavioral constructs, and an *in vivo* measurement of neuroreceptor or transporter availability in humans using PET). Examples include an unpublished study from our research group in which the correlation between mGluR5 availability and impulsivity in BPD and PTSD individuals ranged from 0.46. to 0.80 in frontal and limbic brain regions of interest (n= 56). Observed correlations ranged in magnitude from 0.21 to 0.80 (positive or negative) with a median r = 0.57. Magnitude of relevant correlations observed in our preliminary data are comparable (i.e., correlation between impulsivity and fronto-limbic mGluR5 availability, r = 0.896). We will evaluate aim 2 using correlational analyses. Using a correlation estimate of 0.55 (based on both review of the literature and our pilot data) and a two-tailed  $\alpha = 0.05$ , a priori power analysis suggested we will require a minimum n = 24 to achieve more than 80% power for the planned analysis. As we plan to conduct correlational analyses within the CUD group (n = 30), we will be adequately powered to test this hypothesis. Data Analysis for Hypothesis 2: Correlational analysis (Spearman or Pearson, as appropriate based on observed data distributions) will be used to test for associations between fronto-limbic mGluR5 availability, CUD severity, impulsivity,  $\theta$ - band power and LTP, and working memory performance. Multiple regression analyses will also be considered to control for potential confounding variables. a will be set at 0.05 for all planned correlational analyses. We will also assess for associations between mGluR5 availability and performance on

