Aim 3: Within CUD subjects, to determine changes in mGluR5 availability, EEG, and neurocognition following cannabis abstinence. Hypothesis 3: Following cannabis abstinence: (a) mGluR5 will decrease; (b) theta power/LTP will be increased; (c) memory will improve. Power Calculations for Hypothesis 3: Using the same standards applied for Aims 1 and 2, we considered our preliminary data and conducted a literature review to determine the magnitude of effect sizes we might reasonably expect to observe with respect to change in mGluR5, EEG, and cognition as a function of abstinence from cannabis. Values necessary to calculate associated effect sizes were not provided in the reviewed literature. For example, Hirvonen and colleagues (2012) observed a significant increase in CB1 receptor availability in cannabis users after abstinence in both the PFC and amygdala. While percent change (pre-post abstinence) could be roughly estimated from the figure provided, exact values are not available, preventing effect size estimation. We do not have preliminary data examining participants pre- and postcannabis abstinence. However, we believe that comparison of available PET data showing in vivo mGluR5 availability in current cannabis users compared with former users may be indicative of the magnitude of change we can expect to see following abstinence. Comparison of mGluR5 availability in current and former cannabis users in our preliminary sample (n= 5 per group) showed a large effect (d = -1.2). We will evaluate Hypothesis 3 using repeated measures ANOVA. Using a moderate effect size estimate of d = 0.58 at  $\alpha = 0.05$  (highly conservative relative to the noted relevant finding in our preliminary data), a priori power analysis suggested we will require n = 30 to achieve 80.13% power for the planned analysis. Data analysis for Hypothesis 3: To test Hypotheses 3, we will conduct 3 repeated measures ANOVAs to examine changes pre- and post-cannabis abstinence in n = 30 CUD subjects. Specifically, models will evaluate: (1) changes in mGluR5 availability; (2) changes in  $\theta$ -band power and coherence; (3) changes in cognition pre-post abstinence from cannabis in the CUD group. Variables that differ significantly between groups, including age and sex, will be considered for entry into the models. A statistically significant result indicative of lower mGluR5 availability following abstinence (model 1) or higher  $\theta$ - band power and coherence (model 2) and improved cognition (model 3) will be considered supportive of Hypothesis 3.

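### Aim 1 compares matched groups with an ANOVA that ignores the matching variables and lets a covariate in only after a significant baseline difference; prespecified ANCOVA is a cheap improvement

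*Combined protocol and SAP*

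**What the plan says.** **Matching.** The synopsis (Research Subjects & Recruitment) describes individual matching: "Each HC will be carefully matched to each CUD subject by age, sex, socioeconomic status, education, nicotine use, and other relevant variables". Section 5.1 gives the same list at group level: "Controls will be matched to the CUD group by age, sex, socioeconomic status, education, nicotine use, and other relevant variables". Section 5.2 leaves room for nicotine use to vary, because the substance exclusion reads "Other substance use disorder within 1 year, except for nicotine".

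**Aim 1 analysis.** Under Data Analysis for Hypothesis 1, section 9.2 specifies a univariate ANOVA of mean fronto-limbic V_T on group. It then says "Groups will be carefully matched on demographic variables" and gives one covariate rule: "any demographic variables that differ significantly between groups, including notably age and sex, will be considered for entry as additional fixed factors" (continuous variables would enter as covariates). Hypothesis 1 is judged as follows: "A significant group difference suggestive of higher mGluR5 availability in CUD subjects will be considered supportive of Hypothesis 1". Sections 9.4.1 to 9.4.3 refer back to 9.2 and add no covariate list. Section 9 does not name nicotine.

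**Other aims.** For Aim 2, "Multiple regression analyses will also be considered to control for potential confounding variables". For Aim 3, whose models are pre-post comparisons in the 30 CUD subjects, "Variables that differ significantly between groups, including age and sex, will be considered for entry into the models". Controls are measured at Day 0 only.

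**The concern.** The groups are not randomised, so the primary contrast depends on comparability. The plan builds comparability in by matching and then analyses the data as two independent samples. An ANOVA that omits the matching variables leaves their contribution to V_T in the error term, although matching has already removed it from the difference in means. The standard error is then too large for the design.

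The only route back to adjustment is a baseline significance test followed by discretion. That test asks the wrong question. Bias equals the imbalance multiplied by the covariate's association with V_T, and a p-value at 60 subjects measures neither. When matching succeeds the screen practically never triggers. When matching partly fails it usually misses the imbalance.

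Nicotine shows the gap most clearly: it is important enough to match on, but whether it could enter the model depends on how the analyst reads 'demographic'. At stake are correct error rates, some power, and a primary model fixed before the data are seen.

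**Working it through.** **Inputs from the documents:** 30 per group, two-sided alpha 0.05, d = 0.82, stated power 81.07% (section 9.2).

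**Inputs assumed:** nicotine-V_T correlation r = 0.3 or 0.5 in size; nicotine imbalance of 0.2 or 0.5 SD when matching is imperfect. The documents give neither value, nor the sign of any nicotine effect.

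**1. The plan's own power figure.** Noncentrality is 0.82 × √15 = 3.176, with 58 df and critical t = 2.002. Power is 87.8%, not 81.07%; the stated figure corresponds to 25 per group. The discrepancy is conservative and separate from this point. I use 87.8% as the unadjusted baseline with independent groups and no bias.

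**2. What the screen detects.** The smallest observed imbalance that reaches significance is 2.002 × √(2/30) = 0.517 SD. The probability of detecting a true imbalance, with noncentrality = imbalance × √15, is:
- 0.2 SD: 11.9%
- 0.5 SD: 47.8%

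**3. Matching works.** With close pair matching, the variance of the difference in means shrinks by about 1 − r², but the ANOVA error term does not. The unadjusted test therefore behaves as if its critical value were 2.002/√(1 − r²), with noncentrality 3.176/√(1 − r²). ANCOVA on nicotine has the same noncentrality with the correct critical value (57 df).

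| r | Effective critical value | Type I error, unadjusted | Noncentrality | Power, unadjusted | Power, ANCOVA |
|---|---|---|---|---|---|
| 0.3 | 2.098 | 4.0% | 3.329 | 88.8% | 90.5% |
| 0.5 | 2.311 | 2.4% | 3.667 | 90.9% | 95.0% |

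A simulation of pair matching (40,000 runs per cell, within-pair error SD 0, 0.3 or 0.6) agrees: unadjusted type I error 4.0 to 4.2% and 2.6 to 2.8%, and ANCOVA 4.9 to 5.1%. The screen practically never triggered.

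**4. Matching leaves an imbalance and nicotine is not adjusted for.** Bias in SD units of V_T is imbalance × r. Type I error uses noncentrality bias × √15. Power, when the bias lowers V_T in CUD, uses (0.82 − bias) × √15.

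| Imbalance | r | Bias | Two-sided type I error | Power at d = 0.82, bias lowering V_T |
|---|---|---|---|---|
| 0.2 SD | 0.3 | 0.06 | 5.6% | 82.5% |
| 0.2 SD | 0.5 | 0.10 | 6.7% | 78.3% |
| 0.5 SD | 0.3 | 0.15 | 8.8% | 72.3% |
| 0.5 SD | 0.5 | 0.25 | 15.9% | 58.4% |

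If the bias instead raises V_T in CUD, false support for Hypothesis 1 at 0.2 SD is 4.2 to 5.7%, against a nominal 2.5%.

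**5. The screen reaches nicotine and is always followed** (simulation, 40,000 per cell, bias lowering V_T). Type I error is 4.9 to 5.2% at 0.2 SD and 5.4 to 6.1% at 0.5 SD. Power is 85.1 to 83.3% and 82.7 to 82.1%. ANCOVA in the same cells has type I error 4.8 to 5.2%, with power 89.9 to 94.3% and 88.0 to 93.3%.

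**6. How large is 0.5 SD?** If nicotine use were yes/no with prevalence 30 to 50% (assumed), 0.5 SD is 0.5 × √(p(1 − p)) × 30, or 6.9 to 7.5 more users in one group of 30. At 0.2 SD the excess is 2.7 to 3.0.

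**The case against.** The strongest reply is that matching is the protection and the plan matches on nicotine. That largely stands. A 0.5 SD imbalance means about seven surplus users in one group, which individual matching is meant to prevent and nothing in the documents predicts. A reader might infer from step 4 that Aim 1 carries a 9 to 16% false-positive risk. The documents do not support that; those rows describe matching failure combined with no adjustment.

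Four other stronger readings also fail.
- *Nicotine is barred from the model because it is not demographic.* The wording permits this but does not settle it. Section 9.2 calls the matching demographic, and the matching lists include nicotine. The wider term used for Aim 2 proves little, since the Aim 2 text also speaks of demographic variables. If nicotine can enter and the rule is always followed, type I error stays near 5 to 6%.
- *Matching and adjustment are the only safeguards.* Sections 5.1 and 5.2 also restrict eligibility on psychiatric, medical and substance-use history, and the PET methods hold scan time of day constant.
- *Nicotine goes unrecorded because the schedules of activities omit it.* Those tables list outcomes and omit age and education too; matching on nicotine requires the information.
- *The Aim 3 sentence damages that analysis.* No effect on results is shown.

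It is also fair to say that unadjusted power is already adequate if matching works. What remains is that the analysis does not reflect the design, and covariate entry is left to a weak test and to discretion.

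**Conclusion.** The point holds as a cheap improvement in prespecification and does not invalidate Aim 1. If matching works, the planned ANOVA is conservative: type I error about 4.0 to 2.4%, and power 88.8 to 90.9% where ANCOVA would give 90 to 95%. The harm there is overstated standard errors and lost precision. If matching leaves a modest 0.2 SD imbalance that goes unadjusted, type I error is 5.6 to 6.7%, and power is 83 to 78% if the bias lowers V_T in CUD. All these sizes rest on the assumed correlation of 0.3 to 0.5 and, in the second case, on the assumed imbalance. The detection rates of 12% and 48% need neither assumption about V_T. That the primary model is not fixed in advance follows from the text alone. The Aim 3 sentence is a wording slip: the models it governs have no second group.

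**What to change.** - **Aim 1, section 9.2:** prespecify the primary analysis as ANCOVA of composite V_T on group, age, sex and nicotine use, with nicotine defined as recorded for matching. Delete the significance screen.
- **Sensitivity analysis:** prespecify one that adds socioeconomic status and education, which are also matched on.
- **Aim 3, editorial only:** delete the sentence on variables that differ between groups.

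**Cost:** SAP wording and 3 of 58 error degrees of freedom, leaving 55. Recomputing the step 3 ANCOVA power with 55 rather than 57 df changes it by less than 0.1 percentage point. No new data are needed, provided the nicotine information used for matching is kept in the study database.
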